# Table 14.3.3.5 12-Lead ECG Markedly Abnormal Shifts from Baseline to Worst On-Treatment Result Safety Analysis Set

			Worst On-Treatment Result		
				At Least One Marked	
			No Marked Abnormality	Abnormality	
Parameter	Treatment Group	Baseline Result	n (%)	n (%)	
Any Parameter	HP-3070 18.0 mg (N=XX)	No Marked Abnromality	xx (xx.x)	xx (xx.x)	
		At Least One Marked Abnormality	xx (xx.x)	xx (xx.x)	
	HP-3070 9.0 mg (N=XX)	No Marked Abnormality	xx (xx.x)	xx (xx.x)	
		At Least One Marked Abnormality	xx (xx.x)	xx (xx.x)	
	Placebo (N=XX)	No Marked Abnormality	xx (xx.x)	xx (xx.x)	
		At Least One Marked Abnormality	xx (xx.x)	xx (xx.x)	
QT Interval	HP-3070 18.0 mg (N=XX)	No Marked Abnormality	xx (xx.x)	xx (xx.x)	
		At Least One Marked Abnormality	xx (xx.x)	xx (xx.x)	

Note: ECG = Electrocardiogram, QTcB = QT interval corrected by Bazett's formula, QTcF = QT interval corrected by Fridericia's formula, HR = Heart Rate,

Note: N is the number of subjects with both baseline and post-baseline assessments in a treatment group.

Note: Worst on-treatment result is defined as the worst result occurring after the administration of the first dose of double-blind study medication.

Note: Baseline is defined as the last non-missing measurement taken prior to first dose of double-blind study medication.

Note: Markedly abnormal is defined as an absolute value > 450 msec or a CFB >= 30 msec for parameters QT interval, QTcB interval, or QTcF interval; value >= 100 bpm for HR parameter; value >= 210 msec for PR interval parameter; >=120 msec for QRS interval.

Note: Percentages are calculated as (n/N)\*100.

Noven\HP-3070\XWA17541\Biostatistics\Production\Tables\xxxxx.sas ddmmmyyyy hh:mm Programming note: Repeat for all parameters and treatment groups.

Author: [name]

Version Number:

Version Date:

Draft 2 09Jan2017 Page **96** of **144** 

Page 1 of x

Noven Pharmaceuticals, Inc. STATISTICAL ANALYSIS PLAN: PROTOCOL HP-3070-GL-04

Noven Pharmaceuticals, Inc. Protocol HP-3070-GL-04

			HP-3070 18 0 mg	HP-3070 9 0 mg	Placebo
			(N=xxx)	(N=xxx)	(N=XXX)
Parameter (Unit)	Visit	Statistic	, ,	× /	, ,
Sitting Systolic Blood Pressure					
(mmHg)					
	Baseline	n	XX	XX	XX
		Mean	XX.X	xx.x	XX.X
		SD	XX.XX	XX.XX	xx.xx
		Median	XX	XX	XX
		Min	XX	XX	XX
		Max	XX	XX	XX
	Week 1	n	XX	XX	XX
		Mean	XX.X	XX.X	xx.x
		SD	XX.XX	XX.XX	XX.XX
		Median	XX	XX	XX
		Min	XX	XX	XX
		Max	XX	XX	XX
	Change from	n	XX	ХХ	ХХ
	Baseline to				
	Week 1				
		Mean	XX.X	xx.x	xx.x
		SD	XX.XX	xx.xx	XX.XX
		Median	XX	XX	XX
		Min	XX	XX	хх
		Max	XX	XX	XX

Table 14.3.4.1 Vital Signs Results and Change from Baseline by Visit Safety Analysis Set

Note: Baseline is defined as the last non-missing measurement taken prior to first dose of double-blind study medication. Note: Unscheduled visits are not included in this summary.

Noven\HP-3070\XWA17541\Biostatistics\Production\Tables\xxxxx.sas ddmmmyyyy hh:mm Programming note: Repeat for all visits and all measurements planned in the protocol.

Author: Aman

[name]

Version Number: Version Date: Draft 2 09Jan2017 Page **97** of **144** 

IMS Health & Quintiles are now

Noven Pharmaceuticals, Inc. Protocol HP-3070-GL-04 Page 1 of x

# Table 14.3.4.2 Orthostatic Hypotension by VisitSafety Analysis Set

		HP-3070 18.0 mg	HP-3070 9.0 mg	Placebo
Visit	Statistic	(N=XXX)	(N=xxx)	(N=XXX)
Baseline	Ν	XX	хх	XX
	n (%)	xx (xx.x)	xx (xx.x)	xx (xx.x)
Week 1	Ν	XX	хх	XX
	n (%)	xx (xx.x)	xx (xx.x)	xx (xx.x)
Week 2	Ν	XX	XX	XX
	n (%)	xx (xx.x)	xx (xx.x)	xx (xx.x)
Week 3	Ν	xx	XX	XX
	n (%)	xx (xx.x)	xx (xx.x)	xx (xx.x)
Week 4	Ν	XX	XX	XX
	n (%)	xx (xx.x)	xx (xx.x)	xx (xx.x)
Week 5	Ν	xx	xx	XX
	n (%)	xx (xx.x)	xx (xx.x)	xx (xx.x)
Week 6	Ν	XX	XX	XX
	n (%)	xx (xx.x)	xx (xx.x)	xx (xx.x)

Note: Subjects with a decrease of >= 30 mmHg in Systolic Blood Pressure and/or a decrease of >= 20 mmHg in Diastolic Blood Pressure after >=3 minutes standing compared to the previous supine blood pressure are classified as having orthostatic hypotension.

Note: Percentages are calculated as (n/N) \* 100, where N is the number of subjects with data at the given visit. Note: Unscheduled visits are not included in this summary.

Noven/HP-3070/XWA17541/Biostatistics/Production/Tables/xxxxx.sas ddmmmyyyy hh:mm

Author: [name]

Version Number: Version Date: Draft 2 09Jan2017 Page 98 of 144

Page 1 of x

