# 16.5. VITAL SIGNS

The following Vital Signs measurements will be reported for this study at each visit:

Document:	\\quintiles.net\Enterprise\Apps\sas	data\SASb\SAS\Noven\HP-	
	3070\XWA17541\Biostatistics\Docu	mentation\SAP\Final 6\Noven HP-3070-GL-04 S	AP text Final
	6_18Jan2018.docx		
Author:	[name]	Version Number:	Final 6
		Version Date:	18Jan2018
Template No:	CS_TP_BS016 – Revision 3	Reference: 0	CS_WI_BS005
Effective Date	: 01May2012		

Copyright © 2012 Quintiles Transnational Corp. All rights reserved.

- Sitting, supine, and standing Systolic Blood Pressure [SBP] (mmHg)
- Sitting, supine, and standing Diastolic Blood Pressure [DBP] (mmHg)
- Sitting, supine, and standing Pulse Rate (bpm)
- Respiratory Rate (breaths/min)
- Temperature (°C)
- Weight (kg)

Height (cm) will measured at Screening only.

Subjects with a decrease of  $\geq$ 30 mmHg in SBP and/or a decrease of  $\geq$ 20 mmHg in DBP after  $\geq$ 3 minutes standing compared to the previous supine blood pressure will be classified as having orthostatic hypotension.

The following summaries will be provided for vital signs data:

- Actual and change from baseline by visit
- Number and percentage of subjects with orthostatic hypotension by visit
- Incidence of markedly abnormal values (see Section 16.5.1) by visit

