#### 16.5.1. VITAL SIGNS MARKEDLY ABNORMAL CRITERIA

Markedly abnormal quantitative Vital Signs measurements will be identified in accordance with the following criteria:

Variable	Unit	Low	High
SBP	mmHg	≤ 90 mmHg AND	≥ 180 mmHg AND
		change from baseline ≤ -20 mmHg	change from baseline ≥ 20 mmHg
DBP	mmHg	≤ 50 mmHg AND	≥ 105 mmHg AND
		change from ≤ -15 mmHg	change from baseline ≥ 15 mmHg
Heart rate	bpm	≤ 50 bpm AND	≥ 120 bpm AND
		change from baseline ≤ -15 bpm	change from baseline ≥ 15 bpm
Body	°C	NA	≥ 38.3 °C AND
temperature			change from baseline $\ge 1.1 \degree C$
Weight	Кд	percentage change from baseline ≤ -7.0 %	percentage change from baseline ≥ 7.0 %

 

 Document:
 \\quintiles.net\Enterprise\Apps\sasdata\SASb\SAS\Noven\HP-3070\XWA17541\Biostatistics\Documentation\SAP\Final 6\Noven HP-3070-GL-04 SAP text Final 6\_18Jan2018.docx

 Author:
 [name]
 Version Number:
 Final 6 Version Date:

 Template No:
 CS\_TP\_BS016 - Revision 3
 Reference:
 CS\_WI\_BS005

Effective Date: 01May2012

Copyright © 2012 Quintiles Transnational Corp. All rights reserved.

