#### 16.7.4. SUICIDALITY: COLUMBIA-SUICIDE SEVERITY RATING SCALE

Suicidality will be monitored during the trial using the C-SSRS. This trial will use the "Baseline/Screening" and "Since Last Visit" versions of the scale. The "Baseline/Screening" version, which assesses the lifetime experience of the subject with suicide events and suicidal ideation and the occurrence of suicide events and/or ideation within a specified time period prior to entry into the trial, will be completed for all subjects at the Screening visit to determine eligibility. The "Since Last Visit" C-SSRS form will be completed at Baseline to confirm eligibility (prior to the first dose) and at all post-Baseline visits.

Suicidal Ideation is rated on a 6-point scale from 0="No ideation present" to 5="Active ideation with plan and intent". A score of 4 or 5 on this scale indicates serious suicidal ideation. Any score greater than 0 will be counted as having suicidal ideation.

The Ideation Intensity total score is the sum of five items from the Ideation Intensity scale: frequency, duration, controllability, deterrents, and reasons for ideation. The possible range for the Intensity total score is 0 to 25. If a subject did not endorse any suicidal ideation, a score of 0 for the intensity total score will be given.

Suicidal Behavior is collected as actual attempt, interrupted attempt, and aborted attempt. Any attempt will be defined as suicidal behavior.

The following summaries will be presented:

• Suicidal ideation:

Document:	\\quintiles.net\Enterprise\Apps\sasdata\SASb\SAS\Noven\HP-		
	3070\XWA17541\Biostatistics\Docu	mentation\SAP\Final 6\Noven HP-3070-GL-04 S	AP text Final
	6_18Jan2018.docx		
Author:	[name]	Version Number:	Final 6
		Version Date:	18Jan2018
Template No:	CS_TP_BS016 – Revision 3	Reference: 0	CS_WI_BS005

Effective Date: 01May2012

Copyright © 2012 Quintiles Transnational Corp. All rights reserved.

All C-SSRS data will be presented in a subject listing.

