# Table 14.3.5.4.2 C-SSRS Most Severe Suicidal Ideation and Suicidal Behavior Safety Analysis Set

	HP-3070 18.0 mg	HP-3070 9.0 mg	Placebo
	(N=xxx)	(N=XXX)	(N=xxx)
	n (%)	n (%)	n (%)
Any Suicidal Ideation During Double-Blind Treatment Period	xx (xx.x)	xx (xx.x)	xx (xx.x)
1: Wish to be Dead	xx (xx.x)	xx (xx.x)	xx (xx.x)
2: Non-Specific Active Suicidal Thoughts	xx (xx.x)	xx (xx.x)	xx (xx.x)
3: Active Suicidal Ideation with Any Methods (Not Plan) without Intent to Act	xx (xx.x)	xx (xx.x)	xx (xx.x)
4: Active Suicidal Ideation with Some Intent to Act, without Specific Plan	xx (xx.x)	xx (xx.x)	xx (xx.x)
5: Active Suicidal Ideation with Specific Plan and Intent	xx (xx.x)	xx (xx.x)	xx (xx.x)
Any Suicidal Behavior During Double-Blind Treatment Period	xx (xx.x)	xx (xx.x)	xx (xx.x)
Actual Attempt	xx (xx.x)	xx (xx.x)	xx (xx.x)
Interrupted Attempt	xx (xx.x)	xx (xx.x)	xx (xx.x)
Aborted Attempt	xx (xx.x)	xx (xx.x)	xx (xx.x)
Preparatory Acts or Behavior	xx (xx.x)	xx (xx.x)	xx (xx.x)
Completed Suicide During Double-Blind Treatment Period	XX (XX.X)	xx (xx.x)	xx (xx.x)
Any Ideation or Behavior Suicidality During Double-Blind Treatment Period	xx (xx.x)	xx (xx.x)	xx (xx.x)
Without Ideation or Behavior Suicidality During Screening/Baseline	xx (xx.x)	xx (xx.x)	xx (xx.x)
Both Ideation and Behavior Suicidality During Double-Blind Treatment Period	xx (xx.x)	xx (xx.x)	xx (xx.x)
Without Ideation and Behavior Suicidality During Screening/Baseline	xx (xx.x)	xx (xx.x)	xx (xx.x)

Note: C-SSRS = Columbia-Suicide Severity Rating Scale.

Note: Any Suicidal Ideation is defined as any score greater than 0.

Note: Treatment-emergent suicidal ideation is defined as no suicidal ideation at baseline/screening and any suicidal ideation postbaseline.

Note: Worsening suicidal ideation is defined as most severe suicidal ideation post-baseline more severe than at baseline/screening. Note: Baseline is defined as the last non-missing measurement taken prior to first dose of double-blind study medication.

Note: Percentages are calculated as (n/N)\*100.

Note: Subjects are counted only at their most severe suicidal ideation type and at their most severe behavior type.

Noven\HP-3070\XWA17541\Biostatistics\Production\Tables\xxxxx.sas ddmmmyyyy hh:mm

Author:	[name]	Version Number:	Draft 2
		Version Date:	09Jan2017
			Page 104 of 144

Noven Pharmaceuticals, Inc. Protocol HP-3070-GL-04 Page 1 of x

Table 14.3.6 Summary of Patch Adhesion,	, Adhesive Residue, and Skin Irritation
Safety Ana	lysis Set

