## Listing 16.2.3.4 Vital Signs Safety Analysis Set

Treatment Group: HP-3070 18.0 mg

Subject ID		Date of Assessment				Markedly
Subject ID	Visit	(Period, Study Day)	Parameter/Position	Result	Unit	Abnormal
****	Screening	YYYY-MM-DD (xx, xx)	Oral Temperature	хх	XX	Ν
			Height	xx	xx	Ν
			Weight	xx	xx	Ν
			BMI	xx	Xx	Ν
			Systolic Blood Pressure/ Sitting	xx	xx	Ν
			Diastolic Blood Pressure/ Sitting	xx	xx	Ν
			Pulse/ Sitting	XX	XX	Ν
			Systolic Blood Pressure/ Supine	XX	XX	Ν
			Diastolic Blood Pressure/ Supine	xx	xx	Ν
			Pulse/ Supine	XX	XX	Ν
			Systolic Blood Pressure/ Standing	XX	XX	Ν
			Diastolic Blood Pressure/ Standing	XX	XX	Ν
			Pulse/ Standing	XX	XX	Ν
xxxx-xxxx	Week 1	YYYY-MM-DD (xx, xx)	Oral Temperature	XX	XX	Ν

Note: SB = Single-Blind, DB = Double-Blind, FU = Follow-up.

Note: Sitting indicates 5 minutes sitting, supine indicates 5 minutes supine, and standing indicates 1-3 minutes after standing. Note: During the SB period, study day is calculated relative to the first dose of study medication during the run-in period. During the DB and FU periods, study day is calculated relative to the first dose of double-blind study medication.

Noven\HP-3070\XWA17541\Biostatistics\Production\Listings\xxxxx.sas ddmmmyyyy hh:mm Programming note: Repeat for HP-3070 9.0 mg and Placebo.

Author: Amand

[name]

Version Number: Version Date: Draft 2 09Jan2017 Page **139** of **144** 

Noven Pharmaceuticals, Inc. Protocol HP-3070-GL-04

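### Suicidal behaviour and marked weight loss are defined differently in the SAP text and its table shells, and the standing time for orthostatic hypotension is labelled inconsistently

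*SAP*

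**What the plan says.** **Suicidal behaviour.** SAP Section 16.7.4 states "Suicidal Behavior is collected as actual attempt, interrupted attempt, and aborted attempt" and then "Any attempt will be defined as suicidal behavior". Table 14.3.5.4.2 has a row "Any Suicidal Behavior During Double-Blind Treatment Period", and among the categories beneath it is "Preparatory Acts or Behavior". The screening/baseline page of that table has the same structure. The by-visit Table 14.3.5.4.1 counts subjects with any type of suicidal behaviour, but its footnotes define only ideation.

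**Marked weight loss.** Section 16.5.1 gives the low criterion for weight as "percentage change from baseline ≤ -7.0"%. The shell of Table 14.3.4.3 prints the corresponding row as a change of ≤ 7.0%, directly above the weight-gain row of ≥ 7.0%. Both feed the row *Any Marked Abnormality*.

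**Orthostatic hypotension.** Section 16.5 classifies subjects by a drop of at least 30 mmHg systolic and/or 20 mmHg diastolic after at least 3 "minutes standing compared to the previous supine blood pressure will be classified as having orthostatic hypotension". Table 14.3.4.2 repeats that rule: subjects with such a drop "after >=3 minutes standing compared to the previous supine blood pressure are classified as having orthostatic hypotension". The footnote to Listing 16.2.3.4 describes the reading differently: "standing indicates 1-3 minutes after standing".

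Section 8 makes the templates the source for the format and content of the tables, so the shells are part of the specification.

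**The concern.** Section 2.4 names body weight, vital signs and the C-SSRS as safety objectives. Section 16 plans no between-group tests for safety unless a section says otherwise, so these descriptive counts are themselves the safety result. Where text and shell give different rules, the number reported depends on which one the programmer follows.

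At stake are whether a subject whose only behaviour is a preparatory act counts as showing suicidal behaviour, whether the weight-loss and pooled abnormality rows carry any information, and whether the orthostatic table describes the reading on which it is based.

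**Working it through.** **1. Suicidal behaviour, side by side**

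| Place | Categories counted |
|---|---|
| Section 16.7.4 | actual, interrupted, aborted attempts |
| Table 14.3.5.4.2, both periods | the same three, plus preparatory acts |
| Table 14.3.5.4.1 | any type; no list given |

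The two explicit versions differ by exactly the subjects whose only behaviour is preparatory. The one written definition available for Table 14.3.5.4.1 is that in 16.7.4. If it is used there, those subjects are in the any-behaviour row of Table 14.3.5.4.2 and missing from the behaviour row of Table 14.3.5.4.1. The rows of Table 14.3.5.4.2 for subjects without ideation or behaviour at screening/baseline depend on the same choice, because the definition also sets baseline status. The SAP gives no rate of preparatory-only behaviour, so the difference cannot be sized.

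**2. Weight**

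Let *x* be the percentage change from baseline.

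- Section 16.5.1: loss if *x* ≤ −7.0; gain if *x* ≥ 7.0. Values between are unflagged.
- Table 14.3.4.3 as printed: loss if *x* ≤ 7.0; gain if *x* ≥ 7.0. The union is every value of *x*, and *x* = 7.0 falls in both rows.

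So, without any assumption, every subject with a post-baseline weight change would be counted under *Any Marked Abnormality*.

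For the loss row alone an assumption is needed, because the SAP gives no weight-change distribution. Take *x* as normal with mean *m* and SD *s*; the flagged proportion is Φ((c − m)/s), with c = −7 (text) or c = +7 (shell). For *m* = 1, *s* = 4:

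- text: Φ((−7 − 1)/4) = Φ(−2.0) = 2.3%, or 0.0228 × 204 ≈ 5 subjects per arm;
- shell: Φ((7 − 1)/4) = Φ(1.5) = 93.3%, or 0.9332 × 204 ≈ 190 subjects per arm.

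The 204 is the planned number per arm in Section 3.1, used only for scale. Over *m* from −1 to +3 and *s* from 2 to 5, the text criterion flags about 0% to 12% and the shell criterion about 79% to 100%.

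**3. Orthostatic hypotension**

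| Place | Standing time |
|---|---|
| Section 16.5 | ≥ 3 minutes |
| Table 14.3.4.2 | ≥ 3 minutes |
| Listing 16.2.3.4 footnote | 1–3 minutes |

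The first two agree in thresholds, timing and supine comparator. The listing window meets theirs only at 3 minutes exactly. However, Section 16.5 reports blood pressure by position, Listing 16.2.3.4 has a position column and no elapsed-time column, and no rule excludes a standing reading by minutes. The timings conflict, but no effect on the count follows from the text.

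**The case against.** The strongest reply is that these are editorial slips. The SAP body sets the rules, 16.5.1 is unambiguous on weight, and a row flagging everyone would be noticed in programming. The missing minus sign may be an artefact of converting the PDF to text. That possibility stands and should be checked first. It is not the obvious explanation, since the minus signs in the blood-pressure and heart-rate rows of the same table survived.

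On suicidal behaviour, a reader might infer that preparatory-only subjects disappear from the report. They do not: Table 14.3.5.4.2 gives preparatory acts their own row and counts each subject at the most severe behaviour type, and all C-SSRS data are listed. The by-visit wording, any type of behaviour, could also be read broadly enough to include preparatory acts, in which case the tables agree. The list of summaries in 16.7.4 is incomplete in the text available here, so a further specification there cannot be excluded; the two definition sentences are intact. What remains is that those sentences contradict the shell.

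On orthostatic hypotension, a reader might infer two incompatible definitions, or a count driven towards zero. The documents support neither. The rule is the same in both places that classify subjects, and a near-zero count would need an elapsed-time filter that the SAP does not specify. Only the inconsistent timing label stands.

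**Conclusion.** Two conflicts between text and shell are confirmed, and each changes who is counted.

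- **Suicidal behaviour:** the versions differ by every subject with preparatory acts alone, a number the SAP does not allow one to estimate. Disagreement between the two C-SSRS tables arises only if such subjects exist and Table 14.3.5.4.1 follows 16.7.4.
- **Weight:** as printed, the pooled abnormality row is 100% of subjects with a post-baseline weight. The loss row would be about 79% to 100% instead of 0% to 12% under the assumed distributions. This rests on the shell really lacking the minus sign.
- **Orthostatic hypotension (minor):** the stated timings are inconsistent and the effect on the count is unknown.

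The efficacy analyses, type I error control and sample size are not affected. The point is still worth acting on, because it concerns counts for named safety objectives.

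**What to change.** 1. Choose one list of suicidal-behaviour categories and state it identically in Section 16.7.4, Table 14.3.5.4.2 and, as a new footnote, Table 14.3.5.4.1.
2. Check the source file of Table 14.3.4.3. If the minus sign is absent there, change the weight-loss row to ≤ −7.0% to match Section 16.5.1.
3. Reconcile the standing time in Section 16.5, the footnote of Table 14.3.4.2 and the footnote of Listing 16.2.3.4, so that the table describes the standing reading actually used. The SAP does not settle which timing was intended.

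The cost is a few lines of wording in the SAP text and shells before the tables are programmed. No new data or additional analysis is required.

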## Noven Pharmaceuticals, Inc. STATISTICAL ANALYSIS PLAN: PROTOCOL HP-3070-GL-04

Noven Pharmaceuticals, Inc. Protocol HP-3070-GL-04

Visit/ Abnormality	Statistic	HP-3070 18.0 mg (N=xxx)	HP-3070 9.0 mg (N=xxx)	Placebo (N=xxx)
Overall Post-baseline	N	XX	XX	XX
Any Marked Abnormality	n (%)	xx (xx.x)	xx (xx.x)	xx (xx.x)
Systolic Blood Pressure				
Result <= 90 mmHg and CFB <= $-20$ mmHg	n (%)	xx (xx.x)	xx (xx.x)	xx (xx.x)
Result >= 180 mmHg and CFB >= 20 mmHg	n (%)	xx (xx.x)	xx (xx.x)	xx (xx.x)
Diastolic Blood Pressure				
Result <= 50 mmHg and CFB <= $-15$ mmHg	n (%)	xx (xx.x)	xx (xx.x)	xx (xx.x)
Result >= 105 mmHg and CFB >= 15 mmHg	n (%)	xx (xx.x)	xx (xx.x)	xx (xx.x)
Heart Rate				
Result <= 50 bpm and CFB <= $-15$ bpm	n (%)	xx (xx.x)	xx (xx.x)	xx (xx.x)
Result >= 120 bpm and CFB >= 15 bpm	n (%)	xx (xx.x)	xx (xx.x)	xx (xx.x)
Body Temperature				
Result >= 38.3 C and CFB >= 1.1 C	n (%)	xx (xx.x)	xx (xx.x)	xx (xx.x)
Weight				
CFB <= 7.0%	n (%)	xx (xx.x)	xx (xx.x)	xx (xx.x)
CFB >= 7.0%	n (%)	xx (xx.x)	xx (xx.x)	xx (xx.x)

Table 14.3.4.3 Vital Signs Markedly Abnormal Results by VisitSafety Analysis Set

Note: CFB = Change from baseline.

Note: Baseline is defined as the last non-missing measurement taken prior to first dose of double-blind study medication. Note: Percentages are calculated as (n/N)\*100, where N is the number of subjects with data at the given visit. Note: Unscheduled visits are not included in this summary.

 $\label{eq:loss} Noven\label{eq:loss} Noven\label{label} Noven\label{$ 

Author:	[name]	Version Number:	Draft 2
		Version Date:	09Jan2017
			Page 99 of 144

Page 1 of x

Noven Pharmaceuticals, Inc. STATISTICAL ANALYSIS PLAN: PROTOCOL HP-3070-GL-04

Noven Pharmaceuticals, Inc. Protocol HP-3070-GL-04

		HP-3070 18.0 mg	HP-3070 9.0 mg	Placebo
Visit	Statistic	(N=XXX)	(N=xxx)	(N=xxx)
Baseline	n	XX	XX	XX
	Mean	xx.x	xx.x	XX.X
	SD	xx.xx	xx.xx	xx.xx
	Median	XX	XX	XX
	Min	XX	XX	XX
	Max	XX	XX	XX
Week 1	n	XX	XX	XX
	Mean	XX.X	XX.X	XX.X
	SD	XX.XX	XX.XX	XX.XX
	Median	XX	XX	XX
	Min	XX	XX	XX
	Max	XX	XX	XX
Change from Baseline to Week 1	n	XX	XX	XX
	Mean	XX.X	XX.X	XX.X
	SD	XX.XX	XX.XX	XX.XX
	Median	XX	XX	XX
	Min	XX	XX	XX
	Max	XX	XX	XX

# Table 14.3.5.1 SAS Total Score Results and Change from Baseline by Visit Safety Analysis Set

Note: SAS = Simpson Angus Scale,

Note: The SAS total score is the sum of the scores for all 10 items and ranges between 0 and 40. If one or more items are missing at a visit the SAS total score is missing. Lower values of the SAS total score indicate milder symptoms.

Note: Baseline is defined as the last non-missing measurement taken prior to first dose of double-blind study medication.

Noven\HP-3070\XWA17541\Biostatistics\Production\Tables\xxxxx.sas ddmmmyyyy hh:mm Programming note: Repeat for all visits.

Author: [name]

Version Number: Version Date: Draft 2 09Jan2017 Page **100** of **144** 

## Table 14.3.5.2.1 AIMS Global Severity Score Results and Change from Baseline by Visit

### Safety Analysis Set

This table will be similar to 14.3.5.1.

Footnotes will be:

Note: AIMS = Abnormal Movement Scale,

Note: The AIMS global severity score is the response to "Severity of abnormal movements" found within the global judgments section. Note: The AIMSassessment consists of 10 items describing symptoms of dyskinesia. Each subject is observed unobtrusively while at rest (e.g., in the waiting room). Each item is rated on a 5-point scale, where 0 is the absence of symptoms and 4 is a severe condition. The AIMS Score is the sum of scored movements of the face, oral, extremities, trunk, and the Investigator's judgments. Note: Baseline is defined as the last non-missing measurement taken prior to first dose of double-blind study medication.

